For the analysis of the quantitative measures, descriptive statistics will be used to generate information that will allow for exploring the relationship of these measures to the other study variables being collected (e.g., severity of depression and diabetes) (**Aim 2**). The descriptive data will also allow comparison of these data to other studies that have used these tools. Reliability will be established for each tool at each time point using Cronbach alpha. The current analysis will test *The Global Family Quality of Life Scale-Adult Women Version* and detail its psychometric properties, specifically construct validity and reliability. Descriptive statistics will include mean age, gender, level of education, race and ethnicity. Data from total sample will be analyzed. Regression analysis will be used to address **Aims 2 and 3**. Mediation analyses will be used as appropriate

2. For the sub-study on the Urinary Microbiome, the following analysis was proposed.

Primary Objectives

(1) To determine the FUM composition in women with T2DM using high throughput 16S rRNA gene sequencing & enhanced quantitative urine culture (EQUC), and to determine the FUM's association with LUTS in women with T2DM.

Hypothesis: Among women with T2DM, their FUM composition is a salient predictor of LUTS.

Planned Analyses: To test this hypothesis, LUTS is the response variable and FUM is the primary explanatory variable. FUM will be measured in at least two ways: First as a microbial diversity index (e.g., Shannon, Chao 1) and as an individual microbial taxa count. When diversity indices are used, a log transformation may be applied to adjust for heterogeneity or lack of linearity.

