In this repeated measures study (baseline, 3, and 6 months), a linear mixed effects model will be used to estimate the effect of FUM on patients' LUTS severity score while allowing random intercepts for each participant to account for the within subject correlation engendered by the repeated measurements. Since we are documenting UTIs over the trial, we will also explore the odds of experiencing at least one UTI, to be estimated as a function of the FUM using a generalized linear mixed effects model that also allows random intercepts for each participant; a binomial distribution with logit link will be specified to determine the odds ratio for the FUM diversity index and microbial taxa count. In these models, extreme error variances will be monitored using the ratio of the Pearson chi-square fit statistic over its degrees of freedom. When necessary, UTI may be treated as a count variable

(particularly if there are enough participants experiencing multiple UTI events) and a Poisson distribution with negative binomial link may be used to adjust for observed overdispersion.

(2) To determine the impact of glycemic control on the LUTS and FUM composition in women with T2DM.

Hypothesis: In women with T2DM, the effect of FUM on LUTS *depends* on glycemic control (HBA1C), which may be measured as a continuous or binary (i.e., >7% versus ≤ 7%) variable.

Planned Analyses: Testing this hypothesis is largely a continuation of the investigation specified in prior objective, except that each model will evaluate if any effect of the FUM on LUTS severity *depends* on women's level of glycemic control. Consequently, for this aim, an interaction term between FUM and glycemic control will be estimated for each model specified above. If the interaction is not significant, adjusted estimates will be provided for the effect of FUM on LUTS after controlling for the effect of glycemic control, as well as other salient covariates (e.g., race, age, depression level, body mass index, and concomitant medications).

For both hypotheses, all comparisons, including all possible pairwise interaction terms, will be evaluated using an alpha level of 0.05 and the tests will be two tailed, meaning that an effect in either direction will be interpreted.

Secondary Objective:

To determine whether there is an association between vitamin D status (sufficient, insufficient, and deficient), LUTS, and the FUM.

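### Microbiome sub-study: covariate adjustment of the FUM-LUTS association is pre-specified only when the FUM-by-HbA1c interaction is not significant

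*Combined protocol and SAP*

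**What the plan says.** All of this is in section V.5.b of the combined protocol and SAP, under the sub-study on the Urinary Microbiome.

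- **Objective 1.** The roles of the variables are set out as "LUTS is the response variable and FUM is the primary explanatory variable". For symptom severity, "a linear mixed effects model will be used to estimate the effect of FUM on" the LUTS score, "allowing random intercepts for each participant to account for the within subject correlation engendered by the repeated measurements". A logistic mixed model for at least one urinary tract infection follows the same pattern. No covariate is named. The microbiome enters in more than one form: "FUM will be measured in at least two ways".
- **Objective 2.** Here "an interaction term between FUM and glycemic control will be estimated for each model specified above". No covariate is named for these models either. All comparisons, interactions included, "will be evaluated using an alpha level of 0.05 and the tests will be two tailed".
- **Adjustment.** One sentence of the sub-study plan mentions it: "If the interaction is not significant, adjusted estimates will be provided for the effect of FUM on LUTS", controlling for glycemic control "as well as other salient covariates (e.g., race, age, depression level, body mass index, and concomitant medications".
- **Secondary objective.** The models of vitamin D status against FUM, LUTS and infection list no covariates.

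The plan does not say what happens to the covariates when the interaction is significant.

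**The concern.** Whether HbA1c modifies the FUM-LUTS association and whether age, obesity or medication confounds it are separate questions. A test of the first carries no information about the second, yet the plan lets the first decide whether an adjusted estimate is produced. Two gaps follow.

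1. Objective 1 asks whether FUM predicts LUTS and answers with models that name no covariates. An adjusted version appears only under Objective 2, in one of its two branches.
2. If the interaction is significant, which would be a notable finding for Objective 2, no adjusted estimate is planned.

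The random intercept does not fill either gap. It accounts for correlation among a woman's repeated measurements. The single FUM coefficient still mixes differences between women with changes within a woman, and the between-woman part carries any confounding by stable characteristics. At stake is whether the sub-study's primary association reflects the microbiome or the women's other characteristics.

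**Working it through.** The documents give no sample size, power or effect size for this sub-study, so there is no stated figure to reproduce. The check has three parts.

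**1. Which models have planned covariates**

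| Model or branch | Covariates named |
|---|---|
| Objective 1, LUTS severity on FUM | none |
| Objective 1, infection on FUM | none |
| Objective 2, interaction models | none |
| Objective 2, interaction not significant | glycemic control, with race, age, depression level, BMI and medications as examples |
| Objective 2, interaction significant | nothing stated |

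With no true interaction, the chance that at least one of k independent tests at 0.05 is significant is 1 − 0.95^k:

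- k = 1: 0.05
- k = 2: 0.0975
- k = 4 (two FUM measures, two outcomes): 0.1855

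Many separate taxa would raise it further.

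**2. Effect of omitting a confounder on the FUM main-effect test**

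All inputs are assumptions: n = 150 women; T = 3 visits (matching the plan's baseline, 3 and 6 months); unit variances; FUM ICC 0.5; LUTS ICC 0.6; no true FUM effect; one woman-level confounder correlated r with both FUM and LUTS.

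In a random-intercept fit, the between-woman information has weight

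w = 0.4 / (0.4 + 3 × 0.6) = 0.1818.

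Per woman, the FUM sum of squares is:

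- within: (3 − 1) × 0.5 = 1.0
- between: 3 × (0.5 + 0.5/3) = 2.0
- weighted total: 1.0 + 0.1818 × 2.0 = 1.3636

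The confounder contributes a weighted cross-product of 0.1818 × 3r² = 0.5455r². Hence

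- spurious slope = 0.5455r² / 1.3636 = 0.4r²
- standard error = √(0.4 / (150 × 1.3636)) = 0.0442

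With z = slope / SE, the rejection rate is Φ(−1.96 + z) + Φ(−1.96 − z).

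| r | spurious slope (SD) | z | rejection, formula | rejection, simulated, unadjusted | simulated, confounder in model |
|---|---|---|---|---|---|
| 0.2 | 0.016 | 0.36 | 6.5% | 7.0% | 4.8% |
| 0.3 | 0.036 | 0.81 | 12.9% | 12.7% | 4.8% |
| 0.4 | 0.064 | 1.45 | 30.4% | 29.8% | 5.0% |

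The simulation used 4,000 replicates. A separate simulation of the same set-up gave 6.8%, 13.9% and 34.8% unadjusted, and 5.2%, 5.0% and 4.8% adjusted. With 60 women the SE is 0.0442 × √(150/60) = 0.0699 and the formula gives 5.6%, 8.1% and 15.0%; simulation gave 5.3%, 8.7% and 15.8%.

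**3. Effect on the interaction test**

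Adding HbA1c, correlated with the confounder at the same r, to the repeated-measures set-up leaves the unadjusted interaction test at 4.8%, 5.4% and 5.1%. A single-visit regression (150 women, confounder effect on LUTS of 0.3 to 0.5 SD) gives 4.6% to 6.4% when the confounder acts linearly. It gives 5.6% to 14.3% when a quadratic effect is added, against 5.1% to 6.0% with the linear and quadratic terms in the model.

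**The case against.** The strongest defence is that the sentence describes ordinary hierarchical reporting. When an interaction is present, a single overall FUM effect means little, so it is reasonable to report one only if the interaction is absent. On that reading the condition governs which estimate is shown and says nothing about whether the interaction model contains covariates. Objective 1 calls FUM the primary explanatory variable, which does not exclude others. This stands to the extent that the plan is silent and forbids no adjustment. It does not close the gap: the only covariate list is attached to one branch, and elsewhere the choice is left open until the data have been seen.

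Second, the primary-study paragraph of V.5.b says that all analyses control for body fat, race and season of entry. Its reach is ambiguous, and race might be covered. But it stands under the primary-study heading, in the paragraph on depressive symptoms, and it does not name age, depression level or medications.

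Third, the size rests on assumptions. This is correct. The number of women giving urine is not stated (section V.3.c says only that they may be asked), and the spurious slopes are small, 0.016 to 0.064 SD.

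A reader might infer two stronger points, and the documents support neither. One is that the FUM-LUTS association is never adjusted. The non-significant branch is exactly an adjusted main-effect estimate, and with no true interaction each model would reach it about 95% of the time. The other is that a significant interaction would probably be an artefact of confounding. Under linear confounding the interaction test keeps its level.

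**Conclusion.** The concern holds as a conditional-adjustment rule and a specification gap. Covariates that the plan itself regards as relevant are promised only after a non-significant interaction test, and the Objective 1 and interaction models have none pre-specified.

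The main exposure is the unadjusted FUM-LUTS association, with a false-positive rate of about 7% to 30% under the assumed 150 women, three visits, ICCs of 0.5 and 0.6 and confounder correlations of 0.2 to 0.4. With 60 women it is about 5% to 16%. For the interaction, the deficiency is the missing adjusted estimate; inflation of the test needs a confounder that also acts non-linearly.

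The point is confined to an added observational sub-study. It should be corrected because it concerns that sub-study's primary objectives, but it does not touch the randomised comparison of depressive symptoms.

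**What to change.** State one covariate set in advance for the microbiome sub-study: age, BMI, race, baseline depression level and concomitant medications. Include it in every FUM-LUTS and FUM-by-HbA1c model, whatever the interaction result. Use the interaction test only to decide whether one overall FUM effect or HbA1c-specific effects are reported, both from adjusted models. State also whether the primary study's rule on body fat, race and season extends to the sub-study.

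As an optional sensitivity analysis, enter FUM as the woman's mean and her deviation from it. The within-woman term is free of confounding by time-fixed characteristics, though not by those that change over the visits. This is a choice, not a correction the plan requires.

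The cost is a few sentences in the SAP and a few degrees of freedom. The covariates are already collected through the CES-D, height and weight, the sociodemographic form and the Diabetes Care Profile, which records medications (section V.4).

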Hypothesis (a): Women with T2DM who have less vitamin D will have will have a different FUM composition than those with sufficient vitamin D.

Hypothesis (b): Women with T2DM who have less vitamin D will have will have more LUTS than those with sufficient vitamin D.

Planned Analyses: For this secondary objective, a generalized linear mixed effects model will be used to determine the odds of at least one UTI as a function of ordinal vitamin D status (deficient, insufficient, and sufficient), again allowing random intercepts for each participant to account for within subject correlation due to repeated measurements; these models will specify a binomial distribution with logit link to determine the odds ratio for each pairwise comparison of vitamin D status. As before, extreme error variances will be monitored using the ratio of each model's Pearson chi-square fit statistic over its degrees of freedom. When necessary, a negative binomial link may be used to account for observed over-dispersion. Finally, a linear mixed effects model will be used to estimate the effect of ordinal vitamin D status on patients' FUM indices and microbial taxa count as well as their LUTS symptom severity score, again allowing random intercepts for each participant. For this objective, all model terms will be evaluated using an alpha level of 0.05 and the tests will be two tailed, meaning that an effect in either direction will be interpreted.

To compare vitamin D, LUTS and the FUM, each individual will function as her own control, with the first time point establishing the baseline FUM profile with which to compare the effect of treatment dose at 6 months (endpoint of trial). We will model the outcome using a GLMM, which takes into account the correlation between 2 observations on the same woman. We will determine if there is a change in a women's FUM baseline to end of study by treatment. We will use similar procedures to determine treatment group differences. Similar data analyses will be conducted on the urinary symptoms reported by each participant across time points and between groups.

Exploratory Aim: To examine the relationship of the phage activity with glycemic control, other labs including Urine PH in biobanked urine samples in the laboratory of [name].

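### The urinary microbiome sub-study evaluates its FUM measures, apparently including individual taxa, and all pairwise interactions each at two-tailed 0.05, with no multiplicity control and no stated number of tests

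*Combined protocol and SAP*

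**What the plan says.** All of this is in the combined protocol and SAP, Section V.5.b (Data Analysis), under the urinary microbiome sub-study.

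- **How FUM is measured (Primary Objective 1, Planned Analyses).** In at least two ways: "First as a microbial diversity index (e.g., Shannon, Chao 1) and as an individual microbial taxa count". The indices are examples. The source of the taxa is 16S sequencing and enhanced culture.
- **Outcomes.** For symptoms, "a linear mixed effects model will be used to estimate the effect of FUM on patients' LUTS severity score". For infection, which the plan says it will explore, a logistic mixed model is used "to determine the odds ratio for the FUM diversity index and microbial taxa count".
- **Interactions (Primary Objective 2).** Each of those models is refitted with a FUM-by-glycemic-control term.
- **Error rate, both primary hypotheses.** "all comparisons, including all possible pairwise interaction terms, will be evaluated using an alpha level of 0.05". Testing is two-sided.
- **Error rate, secondary objective.** Vitamin D status is related to UTI, to the FUM indices and taxa count, and to symptom severity, and "all model terms will be evaluated using an alpha level of 0.05 and the tests will be two tailed".

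No adjustment, hierarchy, false discovery rate or single deciding test is given for the sub-study. The number of taxa, the taxonomic level and any prevalence filter are not stated.

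**The concern.** The level of each test is stated, but nothing limits the error across the set of tests. The set could be large, because sequencing data can supply many taxa and each taxon would be tested against two outcomes, with and without an interaction. The first hypothesis, that FUM composition predicts LUTS, sits under the primary objectives and is not labelled exploratory. The plan does not say which FUM measure decides it. A few nominally significant taxa or interactions could therefore be reported as findings when they are what chance alone would produce, and a reader could not tell how many tests lay behind them.

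**Working it through.** **Inputs from the plan**

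- Per-test level: 0.05, two-sided (both statements of alpha in the sub-study).
- FUM measures: Shannon and Chao 1 as example indices, plus the taxa count.
- Outcomes in the primary objectives: LUTS severity, and UTI (explored).
- Terms per model: the FUM main effect and the FUM-by-HbA1c interaction.
- Number of taxa, K: **not given**. It is treated as an assumption below and varied.

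There is no derived figure in the plan to reproduce. For a single test, 1 − 0.95^1 = 0.05, as stated.

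**Step 1: count the tests.** Two readings of the taxa measure are possible.

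- *One test per taxon:* K × 2 outcomes × 2 terms = 4K tests, or 2K for LUTS alone.
- *One richness number:* 3 measures (Shannon, Chao 1, count) × 2 outcomes × 2 terms = 12 tests, or 6 for LUTS alone.

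The secondary objective adds at least one further test per taxon, with taxa as the response to vitamin D status.

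**Step 2: error under independent tests and true nulls.** Chance of at least one false positive = 1 − 0.95^m. Expected false positives = 0.05 × m.

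| Tests m | At least one | Expected number |
|---|---|---|
| 6 | 0.26 | 0.3 |
| 10 | 0.40 | 0.5 |
| 12 | 0.46 | 0.6 |
| 20 | 0.64 | 1.0 |
| 50 | 0.92 | 2.5 |
| 100 | 0.99 | 5.0 |

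In taxa, at four tests each: 5 taxa are 20 tests (0.64), 10 taxa are 40 tests (0.87), and 15 taxa are 60 tests (0.95). For LUTS alone, at two tests each, 5 taxa are 10 tests (0.40) and 10 taxa are 20 tests (0.64). To reach 0.95, m must be at least ln(0.05)/ln(0.95) = 58.4, so 59 tests.

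**Step 3: correlated tests.** Equicorrelated normal test statistics, 20,000 simulated draws, chance of at least one false positive:

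| Correlation | 10 tests | 50 tests | 100 tests |
|---|---|---|---|
| 0.2 | 0.374 | 0.869 | 0.976 |
| 0.5 | 0.290 | 0.615 | 0.777 |
| 0.8 | 0.171 | 0.298 | 0.358 |

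Correlation lowers the chance of any false positive. The expected number stays at 0.05 per null test, so the errors that do occur come in clusters.

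**Step 4: the reference to all pairwise interactions.** The hypothesis needs one interaction, FUM by HbA1c. Read literally, FUM, HbA1c and the five example covariates (race, age, depression level, body mass index, concomitant medications) make 7 variables and 7 × 6 / 2 = 21 pairwise terms per model.

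**The case against.** Several points on the other side carry weight.

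- **The number of taxa is unknown.** A reader might infer that false-positive taxa are nearly certain. The documents do not support that. It takes about 59 or more roughly independent null tests, and the plan gives no count. At 10 tests the figure is 0.40, and with strong correlation it is 0.298 even at 50.
- **The taxa measure is ambiguous.** It is worded in the singular throughout, so one count of taxa per sample is possible. Testing each taxon is still the more natural reading: the word individual attaches to the taxa, the hypothesis concerns composition, and richness is already what Chao 1 estimates. Even on the narrower reading, 12 tests give 0.46.
- **No rule says that one significant taxon is enough.** A reader might infer that the primary hypothesis cannot fail. The plan sets no such decision rule, so that inference goes too far. What remains is that no deciding test is named.
- **The models name only one interaction.** The sentence on pairwise terms sets the level at which such terms are judged and does not list others. The 21 terms in Step 4 are therefore a literal reading, not a stated plan. The wording should still be narrowed, because it permits them.
- **The tiers differ.** UTI is explored and vitamin D status is a secondary objective, so neither should be counted against the primary LUTS hypothesis. This is accepted. LUTS alone still involves 6 tests (0.26) on the narrow reading, or 2K on the natural one.

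**Conclusion.** The concern holds for the sub-study: a per-test 0.05 is applied to FUM measures, interactions and vitamin D status terms without multiplicity control. Its size depends on a number of tests that the plan does not fix. Under independence and true nulls the chance of at least one false positive runs from 0.40 at 10 tests to 0.99 at 100. It is smaller with correlated taxa, and the expected count falls if some associations are real. On every multi-test reading examined it exceeds the nominal 0.05, so the direction is secure even though the magnitude is not. Nothing here bears on the main trial's CES-D analysis.

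**What to change.** In the planned analyses for the primary and secondary objectives of the sub-study:

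1. Say whether the taxa measure means each taxon or one count per sample. Fix the taxa set (taxonomic level and any prevalence filter) before any association is tested.
2. Replace the blanket 0.05 for taxon-level and interaction tests with Benjamini-Hochberg adjusted q-values at a 5% false discovery rate, applied across taxa within each family: taxa predicting LUTS; taxa predicting UTI, labelled exploratory; FUM-by-HbA1c interactions; and vitamin D status predicting taxa. In the last family vitamin D status is the explanatory variable and the taxa are the responses. If a single count is meant, apply the same procedure across the FUM measures in each family.
3. State that FUM by HbA1c is the only interaction tested for the hypothesis.
4. Report the number of tests in each family.

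Naming one diversity index as the primary FUM variable is a further option. It is more debatable, because the hypothesis is about composition, and the change above does not depend on it.

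The cost is SAP wording and a small addition to the code, with no new data. The real downside is lower power for any single taxon. Control is also per family: with four independent families and all nulls true, the chance of a false finding somewhere would be 1 − 0.95^4 = 0.19, which is why the exploratory and secondary labels should be kept.

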a. Criteria for Participation. Inclusion criteria are: 1) women aged 21 and older, 2) having significantly elevated depressive symptoms as measured by a score \geq 16 using the Center for Epidemiologic Studies Depression Tool (CES-D) (118,121) and/or taking antidepressant medication and having a score \geq 12 using the CES-D and/or CES-D score average of \geq 16 of phone screen and face to face screen, 3) type 2 diabetes and under the care of a health care provider, (4) level of vitamin D also known as 25 hydroxyvitamin D, 25 (OH) D less than 32 ng/dl. **Exclusion criteria are:** 1) current alcohol or substance abuse disorders, 2) a history of bipolar depression or any other psychotic disorder, 3) debilitating chronic illness (e.g., cancer, multiple sclerosis), 4) severe complications of diabetes (e.g., blindness or amputation) since these will impact depression, 5) malabsorption disorders (e.g., crohn’s disease, celiac sprue, gastric bypass) since this impacts vitamin D absorption (122), 6) elevated serum calcium since vitamin D may increase serum calcium (123). 7) taking St. John’s Wort unless they stop for 3 weeks prior to enrollment since it can impact mood (124). 8) use of vitamin D supplements (1000 IUS or greater) in past 2 months and unwillingness to discontinue for at least 1 month prior to study 9) Pregnant or planning a pregnancy. 10) Baseline systolic blood pressure greater than 160 mmHG or diastolic greater than 100 mmHG. Having active treatment for depression (e.g., antidepressant therapy) will not be exclusion criteria if the patient has been under treatment for six weeks or more. Similar criteria were used for our pilot.

b. Recruitment. We contacted diabetes centers within a 20 mile radius of LUMC (most are within a 5 to 10 mile radius) with the closest facilities. The diabetes educators provided estimates of potential patients with type 2 diabetes per month. Support letters have been provided by the recruitment sites. To facilitate recruitment, a meeting will be held at each site (with educators and endocrinologists) to discuss the study, review study brochure, procedures for participating, and follow-up information. We used these sites and this recruitment strategy for our pilot and SWEEP study. We will also work with our marketing department for recruitment of study participants.

Diabetes Center Sites	# Patients/Mo	Diabetes Center Sites	# Patients/Mo

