(Palleschi et al., 2014) and (b) Pelvic Floor Distress Inventory (Barber et al., 2001; 2011) which asks about urinary symptoms and is able to classify individuals into categories of urinary continence. (c) Urinary Incontinence Questionnaire to determine impact of this variable on health and quality of life (International Consultation on Incontinence Modular Questionnaire; ICIQ- <http://www.icig.net/structure.html>). (d) Urinary tract history completed by patient or administered during nurse administered physical exam. (2) Assessment of the urine for inflammatory markers in the laboratory of [name] at LUMC. This will be done by biochip for cytokine analysis.

[name] Lab protocol (e-mail 4-12-19_Specimens transported using FEDEX through [name] Lab protocol. Urines stored -80.C and padlocked. Working protocol to isolate and congregate phages from urines in Appendix 2 of protocol.

5. Data Management and Analysis

a. Data Management: The goals of data management are to: (a) ensure that data collected during the study are properly and accurately entered and documented; (b) ensure that data will be stored in an electronic format that will allow the primary investigators of the project to retrieve data easily and to export data to statistical packages; and (c) ensure the confidentiality of subjects. After the data are entered and checked, several data quality checks will also be conducted, including descriptive statistics and graphic plots to detect outliers and influential observations. All computer data will be stored in a password-protected network server with back-up. The original raw data will be stored in a locked cabinet accessed only by key project personnel. We will run univariate and bivariate analyses for all variables prior to our main analyses. We will evaluate continuous variables using t-tests or F-tests and categorical variables using χ^2 . We will examine data distributions and test all variables for linear relationships or non-linear relationships. Descriptive statistics (means, standard deviation, frequency) and correlations (both Pearson and Spearman) between variables will be conducted to preliminarily assess the data. Necessary transformations and imputations will be conducted on based the raw data.

b. Data Analysis: The conceptual relations in the model for the study (Figure) are being used to guide the testing of the primary, secondary, and exploratory outcomes.

SUNSHINE PRIMARY STUDY:

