Other Exploratory Analysis: We will be able to make comparisons of the FUM with persons who do not have diabetes. Drs. [name] and [name] have sequence and culture data from healthy and incontinent (UUI) women from their prior cohort studies (see **Fig. 2**) (Hilt et al., 2014; Pearce et al., 2014). In addition, 180 well-characterized UITN subjects are adult women with stress urinary incontinence (SUI) that have had clean catch midstream voided urine sequenced (see **Fig. 1**) (Thomas-White et al., 2016b). Thus, comparisons with these

data offer a unique opportunity to determine the impact of having the comorbid condition of diabetes on urinary outcomes to those who do not have diabetes.

c. Missing Data. Item missing data (e.g., a subject fails to answer a particular questionnaire item), will be imputed using procedures such as EM algorithm. For unit missing data (where a subject is missing at a data collection time point), we will determine whether missing data are MCAR (data are missing completely at random), MAR (data are missing at random), or NMAR (not missing at random). If missing data are MCAR or MAR, it is likely that the standard multivariate computations will not result in biased standard error estimates. However, if missing data are NMAR, we will use the "pattern mixture" approach to compute a "weighted average" of the parameters that are associated with the missing data to estimate what the data would have been (157).

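### The outside-cohort comparison cannot show the impact of diabetes on urinary outcomes, because trial women and comparators differ in more than diabetes

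*Combined protocol and SAP*

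**What the plan says.** The text is in section V.5.b (Data Analysis), sub-study on the Urinary Microbiome, under Other Exploratory Analysis. It opens: "We will be able to make comparisons of the FUM with persons who do not have diabetes". Three outside groups are named. Two come from investigators who "have sequence and culture data from healthy and incontinent (UUI) women from their prior cohort studies". The third is a set of 180 "adult women with stress urinary incontinence (SUI) that have had clean catch midstream voided urine sequenced". The paragraph concludes that these data offer "a unique opportunity to determine the impact of having the comorbid condition of diabetes on urinary outcomes".

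The paragraph does not say which trial visit supplies the urine. It gives no model, matching or covariates, and does not say whether the three groups are to be compared separately or pooled.

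**The concern.** The stated aim attributes a difference to diabetes; it goes beyond describing how cohorts differ. That needs the groups to be alike in other respects that affect the urinary microbiome and urinary symptoms, or a plan for handling the differences. Here the trial women were chosen on two further conditions and then given a supplement. Most of the named comparator groups were chosen for a urinary condition, which lies in the same domain as the outcome. If the paragraph is followed as written, a difference produced by depression, vitamin D status, supplementation, continence status or cohort source could be read as an effect of diabetes. Against incontinent women, a real effect of diabetes on symptoms could also be hidden.

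**Working it through.** The plan gives no sample size, effect size or test for this comparison, so there is no figure to reproduce. The check sets the sections side by side.

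| Feature | Trial women | Outside cohorts, as described |
|---|---|---|
| Depressive symptoms | Required for entry: "having significantly elevated depressive symptoms as measured by a score" of 16 or more on the CES-D, or one of two alternatives (V.2.a) | Not stated |
| Vitamin D | 25(OH)D below 32 required (V.2.a; VI.A(1)) | Not stated |
| Supplement | Weekly vitamin D in both arms, 50,000 or 5000 IU (V.1; VI.A(1)) | Not stated |
| Continence | Not an entry criterion; measured by questionnaire | One healthy group, one with urge and one with stress incontinence |
| Urine specimen | Clean-catch midstream (V.3.c) | Clean-catch midstream stated for the stress-incontinence group only |
| Time of urine | Baseline, 3 and 6 months (V.4, table) | Not stated |

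**1. Does the plan itself treat these factors as relevant?** Yes. Under the Secondary Objective in V.5.b, hypothesis (a) expects women with less vitamin D to have a different microbiome, and hypothesis (b) expects them to have more urinary symptoms. The same section will test whether the microbiome changes from baseline to the end of the study by treatment. Primary objective (2) lists depression level and body mass index among its covariates, but only for models within women with type 2 diabetes. Section II calls an effect of vitamin D on urinary symptoms plausible.

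**2. Which samples are affected by supplementation?** The supplement is dispensed at the second visit (V.3.c). Baseline urine can precede it; 3- and 6-month urine cannot. The comparison is not limited to baseline.

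**3. How many comparators were selected for incontinence?** By group, 2 of 3. By head count, let U be the number with urge incontinence and H the number of healthy women. The incontinent share is (180 + U) / (180 + U + H), which exceeds one half when H < 180 + U. Even with U = 0, any H below 180 gives a majority. Neither U nor H is stated, so a head-count majority is likely but not confirmed.

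**4. How certain is the selection on vitamin D?** It is certain for randomized women. The level is reviewed only after the first visit (V.3.c), and urine is listed at baseline and at visit 2 (V.4, table). V.5.d reports 83 of 169 enrolled women randomized: 83/169 = 49.1%, matching the stated 49% and leaving 169 - 83 = 86 who were not. First-visit urine may therefore include women with higher levels.

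**5. Can the bias be sized?** Suppose a factor present in all randomized women shifts a microbiome index by s and is present in a share p of comparators. The spurious difference is s x (1 - p): equal to s if p = 0, and zero if p = 1. The documents give neither s nor p for depression or vitamin D, so its direction and size are both open.

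**The case against.** The strongest reply is that this is one paragraph, labelled exploratory, worded as an opportunity, with no hypothesis or decision attached. It touches no primary or secondary trial conclusion. Detail on the cohorts may also sit in figures and papers that are not available here, including the specimen type of the healthy and urge-incontinence groups. All of that stands, and it limits the weight of the point. An exploratory label excuses low precision and loose error control, but it does not make the attribution to diabetes valid.

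The plan also never says that the three comparator groups will be pooled. Kept apart, they could be informative, and a healthy group is among them. Using that group alone would remove selection for incontinence, though not the differences in depression, vitamin D or source. The plan does not make that restriction.

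A reader might infer that diabetes is completely confounded with depression and low vitamin D. The documents do not support that: they give no data on either factor in any comparator, and some comparators may well have them. Section I itself says that women in general can have low vitamin D levels. Nor can a false-positive rate be put on the comparison, because no sample size, test or effect size is stated for it.

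Finally, matching on continence looks like an obvious remedy, since a pelvic-floor questionnaire already collected "is able to classify individuals into categories of urinary continence". But section II links overactive detrusor activity to diabetes. Continence may thus be a consequence of diabetes, and conditioning on it could remove part of the effect sought. This part of the objection is right.

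**Conclusion.** The concern holds in a limited form. A difference between trial women and the named cohorts cannot be attributed to diabetes alone. It may also reflect depressive symptoms, vitamin D status, supplementation if post-baseline urine is used, continence status or cohort source. The conclusion rests on the entry criteria, on both arms being supplemented, and on the sub-study's own hypotheses about vitamin D. No outside evidence is needed.

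The size is unknown. Two of three comparator groups are defined by incontinence, with a head-count majority unconfirmed, and selection on vitamin D is certain only for randomized women. The point is a cheap improvement to an exploratory analysis.

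**What to change.** Revise the Other Exploratory Analysis paragraph as follows.

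- Use only trial women's baseline urine, collected before the first supplement, and say whether women who were not randomized are included.
- Use only comparators with the same specimen type.
- Report the healthy, urge-incontinence and stress-incontinence comparisons separately, without pooling.
- Adjust for age and body mass index where the outside cohorts hold them.
- Replace the claim about the impact of diabetes with a descriptive difference between cohorts, stated to be inseparable from depression, vitamin D status and cohort source.
- If a comparison within continence category is wanted, make it at most a sensitivity analysis and state that continence may itself be affected by diabetes.

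The cost is one reworded paragraph and a little extra analysis, with no new data collection. Using fewer samples and smaller comparator groups will widen the intervals somewhat.
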